9.2.2 Day 1 of Cycle 1 (C1D1:PK sub study patients)

The following procedures will be performed at C1D1 for patients participating in the PK sub study:

Pre-dose Assessments	Post-dose Assessments

 • Complete physical examination • Weight • ECOG Performance status • Vital signs (BP, pulse, and temperature) • Concomitant medications • Hematology (including reticulocyte count) and serum chemistry • Urinalysis • Blood sampling for ctDNA analysis • Blood sampling for biomarker analysis • Blood sampling for pharmacogenomics analysis • AE monitoring • Lucitanib will be dispensed to the patient • 12-lead ECG (in triplicate, 10-sec tracings >2 min apart) 5–10 min prior to dosing • QoL Questionnaire (FACT-B) • PK blood sample (5–10 min prior to dosing) 	
 • 12-lead ECG (in triplicate, 10-sec tracings >2 min apart), 2 hours (± 5 min) following dosing with lucitanib • AEs experienced by the patient since dosing will be documented • Concomitant medications administered since dosing will be recorded • PK blood sampling collected at the following time points: 15 (± 2) min, 30 (± 3) min, 1 hr (± 5 min), 1.5 hr (± 5 min), 2.5 hr (± 10 min), 4 hr (± 15 min), 6 hr (± 15 min), 8 hr (± 15 min), 10 hr (± 30 min) (optional), and 24 hr (± 30 min) • Vital signs (BP, pulse, and temperature) after last PK sample

9.2.3 Day 1 of Cycle 1 (C1D1; all patients with exception of PK sub study)

Patients will be required to take their first dose of lucitanib at the clinic and within 3 days of enrollment. The following procedures will be performed on C1D1 for all patients with exception of those in the PK sub study:

Pre-dose Assessments	Post-dose Assessments

 • Complete physical examination • Weight • ECOG performance status • Vital signs (BP, pulse, and temperature) • Concomitant medications • Hematology (including reticulocyte count) and serum chemistry • Urinalysis • Blood sampling for ctDNA analysis • Blood sampling for biomarker analysis • Blood sampling for pharmacogenomics analysis • AE monitoring • Lucitanib will be dispensed to the patient • 12-lead ECG (in triplicate, 10-sec tracings >2 min apart) 5–10 mins prior to dosing • Quality of Life (QoL) Questionnaire (FACT-B) 	
 • 12-lead ECG (in triplicate, 10-sec tracings >2 min apart), 2 hours (±5 min) following dosing with lucitanib • AEs experienced by the patient since dosing will be documented • Concomitant medications administered since dosing will be recorded •

9.2.4 Day 4 of Cycle 1 (C1D4; all patients)

The following procedures will be performed during the visit.

Assessments

• Brief history and review of AEs• Weight• Vital signs (BP, pulse, and temperature)• Urinalysis• AE monitoring• Review and collection of BP diary

9.2.5 Day 15 of Cycle 1 (C1D15; all patients)

The following procedures will be performed during the visit. Patients will be instructed to refrain from taking their dose of lucitanib at home on the day of their clinic visit.

Assessments

• Brief history and complete physical examination• Weight• Vital signs (BP, pulse, and temperature)• Hematology (including reticulocyte count) and serum chemistry• Urinalysis• AE monitoring• Pre-dose blood sampling for ctDNA analysis• Pre-dose blood sampling for PD analysis• Pre-dose blood for sparse PK sampling

9.2.6 Day 1 of Cycle 2 (C2D1) and Subsequent Cycles (all patients)

Patients will be instructed to refrain from taking their dose of lucitanib at home on the day of their clinic visit because the dose will be taken during the clinic visit.

The following procedures will be performed pre-dose and post-dose at C2D1 and subsequent visits:

Pre-dose Assessments	Post-dose Assessments

 • Complete physical examination • Weight • ECOG performance status • Vital signs (BP, pulse, and temperature) • Concomitant medication since last visit • Hematology (including reticulocyte count) and serum chemistry • Urinalysis • Blood sampling for ctDNA analysis • Blood sampling for biomarker analysis • AE monitoring • 12-lead ECG (in triplicate, 10-sec tracings >2 min apart) 5–10 mins prior to dosing • LVEF (ECHO or MUGA) – every 8 weeks post-C2D1 • Blood for sparse PK sampling (Day 1 of Cycles 2, 3, and 5) • QoL Questionnaire (FACT-B) on Day 1 of Cycles 3, 5, and 7. After Cycle 7, questionnaires will be collected every 3 cycles (on Day 1, Cycles 10, 13, 16 etc.) • Lucitanib will be dispensed to the patient 	
 • 12-lead ECG (in triplicate, 10-sec tracings >2 min apart), 2 hours (±5 min) following dosing with lucitanib • AEs experienced by the patient since dosing will be documented • Concomitant medications administered since dosing will be recorded • PK sample 1–3 hours post-dose on Day 1 of Cycle 2

Other assessments required during the visit and irrespective of dosing are:

- Tumor assessments will be performed at Cycle 2, Day 1 and thereafter every 8 ± 1 weeks until Cycle 6 and thereafter every 12 ± 1 weeks until tumor progression (see [Section 9.5.2.1](#))
- Review and Collection of BP and dosing diary

9.2.7 Day 15 of Cycle 2 (C2D15; all patients)

The following procedures will be performed during the visit.

Assessments

• Brief history and review of AEs• Weight• Vital signs (BP, pulse, and temperature)• Urinalysis• AE monitoring

9.3 End-of-Study Visit (all patients)

The following procedures will be performed for all patients 28 days (± 7 days) after the last dose of protocol-specified treatment:

- Complete physical examination
- Weight
- ECOG performance status
- Vital signs (BP, pulse, and temperature)
- Concomitant medications since last visit
- Contraceptive counseling
- Serum pregnancy test for women of childbearing potential
- Hematology (including reticulocyte count), and serum chemistry
- Urinalysis
- Tumor scans (using the same methodology as was used at screening), including brain scans for patients with brain lesions at baseline, unless it has been < 2 weeks since last scan or disease progression was noted on the last scan
- Blood sampling for ctDNA analysis
- Blood sampling for biomarker analysis
- AE monitoring (until 28 days after last dose of protocol-specified treatment; all ongoing SAEs should be followed until resolution or stabilization. After the 28-day window, only new SAEs assessed as related to study drug should be recorded)
- Review and collection of BP and dosing diary
- 12-lead ECG (in triplicate, 10-sec tracings > 2 min apart)

- LVEF (ECHO or MUGA)
- QoL questionnaire (FACT-B)
- Survival status
- Subsequent therapies for breast cancer
- Optional post-treatment biopsy for PD analyses, at time of disease progression and before subsequent anti-line therapy is initiated

9.4 Two Monthly Follow-Up (All Cohorts)

- Survival status
- Subsequent therapies for breast cancer

9.5 Methods of Data Collection

9.5.1 Safety Evaluations

9.5.1.1 Adverse Event Assessment

The investigator has the responsibility for assessing the safety of the patients and for compliance with the protocol to ensure study integrity. Patients will be monitored for AEs from the time of first dose of lucitanib through 28 days after the last dose of protocol-specified treatment. Study-procedure-related AEs that occur after signing of the ICF and before administration of lucitanib will also be collected. Any ongoing SAEs will be followed until resolution or stabilization. AEs and laboratory abnormalities will be graded according to the NCI CTCAE Version 4.03 [55] grading system and recorded in the eCRF.

Complete details for monitoring AEs, including the definition of drug-related AEs, are provided in [Section 10](#).

9.5.1.2 Clinical Laboratory Investigations

Certified local laboratories will perform study-related clinical laboratory tests according to institutional procedures, and the results will be reviewed by the investigator. The panels of laboratory tests to be performed are shown below:

Hematology: Hemoglobin, hematocrit, WBC and differential (with ANC), platelet count, PT/PTT, and reticulocyte count per the schedule of evaluation at screening, during treatment, and at the end-of-study visit. Hematology results must be reviewed by the investigator prior to the start of treatment with lucitanib.

Clinical Chemistry: TSH, T3, T4, total protein, albumin, creatinine, BUN or urea, total bilirubin, alkaline phosphatase, ALT, AST, glucose, sodium, potassium, chloride, CO₂, calcium, magnesium, and phosphorus per the schedule of evaluations at screening, during treatment, and at the end-of-study visit. Total cholesterol will be performed at screening only.

Urinalysis: Performed on freshly voided clean sample by dipstick for protein, glucose, blood, pH, and ketones per the schedule of evaluations. If dipstick findings are abnormal, then a microscopic evaluation will be performed to assess the abnormal findings. Urinalysis will be performed at screening, during treatment, and at the end-of-study visit.

Serum Human Chorionic Gonadotropin β (β -hCG) Pregnancy Test: Performed on women of childbearing potential ≤ 7 days prior to administration of the first dose of lucitanib, and at the end-of-study visit. If the serum pregnancy test results are not available prior to the first dose of lucitanib, a urine pregnancy test can be performed to confirm that the patient is not pregnant prior to dosing. Both values should be entered in the eCRF. A negative result must be confirmed by a physician before the first dose of lucitanib can be administered.

Laboratory reports will be reviewed by the investigator or delegated physician to assess clinical significance. Clinically significant abnormalities should be documented in the eCRF as an AE as defined in [Section 10.4](#).

9.5.1.3 Vital Signs

Vital signs will include BP, pulse, and body temperature. All vital signs will be obtained after the patient has been resting for at least 5 minutes. Vital signs will be performed at screening and at each study visit, including the end-of-study visit.

BP self-monitoring should be completed at least twice a week by patients and measurements should be recorded in their diaries and brought to the clinic visits for review. For the week following the first dose of lucitanib, patients are encouraged to record BP in their diary at least once, but preferably twice, prior to their C1D4 visit. After review, the investigator will consider whether the readings require medical treatment or reporting as an AE. Patients are instructed to contact the investigator, if BP values equal or above 160 mmHg systolic and/or equal or above 100 mmHg diastolic. Equipment and guidance to the patients on how to self-monitor their BP will be provided by the sponsor.

9.5.1.4 12-Lead Electrocardiograms

Serial 12-lead ECGs (10-sec ECG tracings collected in triplicate [>2 minutes apart]) will be taken at the following time points and as clinically indicated:

All cohorts:

- Screening: anytime during the screening period
- Day 1 of each treatment cycle: Pre-dose (5–10 minutes prior to dosing) and 2 hours (± 5 min) following dosing with lucitanib
- End-of-Study: Any time after dosing has been discontinued, but within 28 days of last dose

PK Sub Study:

- Day -7: Pre-dose (5–10 minutes prior to dosing) and 2 hours (\pm 5 min) after dosing with the lucitanib tablet formulation

ECGs should be performed after the patient has been resting for at least 5 minutes. The 12-lead ECGs collected will be analyzed at a central ECG laboratory. Details on recording ECGs and preparation for central interpretation will be included in the investigator's file.

9.5.1.5 LVEF

LVEF will be assessed by ECHO or MUGA at screening, on Day 1 of Cycle 2 and every 8 weeks thereafter, and at the End-of-Study. It is recommended to use the same technique for a given patient throughout the whole study duration. ECHO/MUGA results will be analyzed locally.

9.5.1.6 Body Weight and Height

Height will be measured during the screening visit only. Weight will be measured at all clinic visits (the patient should be in light indoor clothes).

9.5.1.7 Physical Examinations

Physical examinations will include an assessment of all the major body systems. Complete physical examinations will be performed at screening, Day -7 (PK sub study only), Day 1 of each cycle, C1D15, Day 1 of each cycle, and at the end-of-study visit.

9.5.1.8 ECOG Performance Status

ECOG performance status ([Appendix B](#)) will be assessed at screening, Day -7 (for patients participating in the PK sub study only), and on Day 1 of each cycle during treatment, and at the end-of-study visit. ECOG performance status should be assessed by the same study personnel at each visit, if possible. Care will be taken to accurately score performance status, especially during screening for study eligibility purposes. Additional consideration should be given to borderline ECOG performance status to avoid enrolling patients with significant impairment.

9.5.2 Efficacy Evaluations

9.5.2.1 Tumor Assessments

The first on-treatment scan should be completed on Cycle 2, Day 1, and every 8 ± 1 weeks through Cycle 6 (i.e., C4D1, C6D1). Thereafter, scans should be completed every 12 ± 1 weeks (i.e., C9D1, C12D1, C15D1, etc.) until disease progression. All patients must have scans to confirm radiographic progression. Tumor scans do not need to be repeated at end-of-study if <2 weeks since last scan or the patient had disease progression at the last scan. Patients that permanently discontinue lucitanib should continue scans until radiographic disease progression. Scans will be evaluated locally for patient treatment decisions. Copies of tumor scans will be

collected centrally to facilitate independent evaluation if subsequently required. Tumor response will be interpreted using RECIST Version 1.1 ([Appendix A](#)).

Tumor assessments should consist of clinical examination and CT scans of the chest, abdomen, and pelvis with intravenous contrast and appropriate slice thickness per RECIST Version 1.1; other alternative studies (MRI and X-ray) may be performed if clinically indicated. The same methods used to detect lesions at baseline are to be used to follow the same lesions throughout the clinical study.

Brain imaging is required at baseline. Patients with brain lesions detected at baseline require repeat brain imaging as part of the follow-up tumor assessments. The same methods used to detect brain lesions at baseline are to be used to follow the lesions throughout the clinical study.

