5.1.3 End-of-Study

All patients should return to the clinic for end-of-study assessments 28 (± 7) days after the last dose of lucitanib has been administered.

The trial will be completed when all enrolled patients have discontinued treatment and completed the end-of-study follow-up visit.

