5.1.4 Long Term Follow-Up

[figure not shown]
All patients will be followed at approximately two monthly intervals to determine survival status, until death or sponsor decision to end the trial, whichever comes first.

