9 STUDY PROCEDURES

[Table 4](#) summarizes the procedures and assessments to be performed for patients in Cohorts A, B and C with exception of patients in the PK sub study; [Table 5](#) summarizes the procedures and assessments to be performed for patients in the PK sub study.

Unless specified, all procedures and assessments are to be completed within ± 2 days of the scheduled time point and are synchronized with administration day of lucitanib.

Table 4: Schedule of Assessments (All Cohorts)

		Treatment Period (Daily Dosing) ^A						
		Cycle 1			Cycle 2 and Beyond	Cycle 2 Only		
Procedure ^B	Screening	Day 1 ^C	Day 4	Day 15	Day 1	Day 15	End-of-Study	Two Monthly Follow-Up
Informed Consent	X							
Medical/Oncology History	X							
Brief History			X	X		X		
Complete Physical Examination	X	X		X	X		X	
ECOG Performance Status	X	X			X		X	
Vital Signs, Height, Weight ^D	X	X	X	X	X	X	X	
Prior/Concomitant Medications and Procedures	X	X			X		X	
Contraceptive Counseling ^E	X						X	
Serum Pregnancy Test ^F	X						X	
Hematology, Including Reticulocytes ^G	X	X		X	X		X	
Serum Chemistry ^H	X	X		X	X		X	
Urinalysis ^I	X	X	X	X	X	X	X	
Tumor Scans (Including brain imaging for patients with known CNS metastases or when clinically indicated) ^J	X				X		X	
Submit FFPE Tumor Tissue ^K	X						X	
Adverse Events ^L	X	X	X	X	X	X	X	
Lucitanib Dispensation/Administration		X			X			
ECG Assessments ^M	X	X			X		X	
LVEF (ECHO or MUGA) ^N	X				X		X	
Plasma for ctDNA Analysis ^O	X	X		X	X		X	
Plasma PD Biomarker Sampling ^P	X	X		X	X		X	

		Treatment Period (Daily Dosing) ^A						
		Cycle 1			Cycle 2 and Beyond	Cycle 2 Only		
Procedure ^B	Screening	Day 1 ^C	Day 4	Day 15	Day 1	Day 15	End-of-Study	Two Monthly Follow-Up
Blood for Sparse PK Sampling ^Q				X	X			
Pharmacogenomic Blood Sampling		X						
Quality of Life Questionnaire ^R		X			X		X	
Review and Collection of BP and Dosing Diary		X	X		X		X	
Survival Status							X	X
Subsequent Therapies for Breast Cancer							X	X

^A Lucitanib will be administered daily, at least 2 hours before and 2 hours after a meal (on an empty stomach) with water (240 mL or 8 ounces). The total fasting period is 4 hours.

^B Unless specified, procedure is completed ±2 days of scheduled time point. Procedures for C1D4 must be completed ±1 day of scheduled time point.

^C Procedures required prior to lucitanib administration on C1D1 may be omitted if completed ≤3 days earlier during the screening period.

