^J Tumor scans obtained within 28 days prior to C1D1, may be used as the baseline scans. Scans should preferably be CT scans of the chest, abdomen, and pelvis with intravenous contrast and appropriate slice thickness per RECIST Version 1.1, using the same methods throughout the study that were used to detect lesions at baseline. Other alternative studies (MRI, X-ray) may be performed if clinically indicated. Brain imaging is required at baseline and must be repeated at follow-up tumor assessments for patients with brain lesions. The first on-treatment scan should be completed on C2D1, and every 8 ± 1 weeks through Cycle 6 (i.e., C4D1, C6D1). Thereafter, scans should be completed every 12 ± 1 weeks (i.e., C9D1, C12D1, C15D1, etc.) until disease progression. Tumor scans do not need to be repeated at End-of-Study if <2 weeks since last scan or the patient had disease progression at the last scan. Scans will be evaluated locally for patient treatment decisions. Scans will be sent to a central radiological laboratory.

^K For patient selection, *FGFR1* and 11q amplification status may be determined based on local assessment, or based on central assessment as confirmed by a prescreening process. FFPE tumor tissue is required for all enrolled patients. The post-treatment biopsy is optional and requires additional consent. Detailed sample handling instructions are provided in the Laboratory Manual.

^L AEs will be assessed from the time of first dose of lucitanib through 28 days after the last dose.

^M ECGs will be taken in triplicate anytime during screening, pre-dose (5–10 mins prior to dosing), and approximately 2 hrs (± 5 mins) post-dose on Day 1 of each Cycle, and at End-of-Study, any time after treatment is discontinued.

^N LVEF will be assessed by ECHO or MUGA. It is recommended to use the same technique for a given patient throughout the study. ECHO should be performed at Screening, on C2D1, and every 8 weeks thereafter, and at the End-of-Study.

^O Whole blood will be collected pre-dose and processed locally for plasma ctDNA. Collections occur at screening, C1D1, C1D15, Day 1 of all subsequent Cycles, and End-of-Study. Refer to the Laboratory Manual for sample handling instructions.

^P Whole blood will be collected pre-dose and processed locally for plasma for PD biomarkers. Refer to the Laboratory Manual for sample handling instructions.

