12 PATIENT DISPOSITION

12.1 Patient Discontinuations

A patient must be discontinued from protocol-prescribed therapy if any of the following apply:

- Consent withdrawal at the patient's own request or at the request of their legally authorized representative
- Progression of patient's underlying disease, unless in the opinion of the investigator and approved by the sponsor, the patient has indolent progression with evidence of continued clinical benefit from treatment. This must be approved by the sponsor and reviewed on a case by case basis
- Any event, adverse or otherwise, that, in the opinion of the investigator, would pose an unacceptable safety risk to the patient
- An intercurrent illness that, in the opinion of the investigator, would affect assessments of the clinical status to a significant degree and requires discontinuation of therapy
- A positive pregnancy test at any time during the study
- Major non-compliance that may affect patient safety
- Investigator decision

In addition, the sponsor may discontinue the trial early for any of the reasons noted in [Section 13.6](#).

The sponsor (or designee) should be notified of all study terminations as soon as possible. The date and reason for cessation of lucitanib must be documented in the eCRF and source documents.

To the extent possible, end-of-study procedures should be performed on all patients who receive lucitanib. The end-of-study visit should occur 28 ± 7 days following the last dose of lucitanib. After stopping protocol-specified treatment, all patients will remain in the study and will be followed for safety (through 28 days after last dose; those with ongoing SAEs will be followed until either resolution or stabilization has been determined), and for survival status by telephone (at approximately two monthly intervals, until death).

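### Scans to progression after stopping lucitanib are required in the text but absent from the follow-up schedule and cut off by the completion rule, leaving primary PFS open to informative censoring

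*Protocol*

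**What the plan says.** **The requirement.** Protocol 9.5.2.1 states: "Patients that permanently discontinue lucitanib should continue scans until radiographic disease progression". The synopsis (Efficacy Assessments) says the same. The tumor-scan footnote to Tables 4 and 5 adds: "Thereafter, scans should be completed every 12 ± 1 weeks (i.e., C9D1, C12D1, C15D1, etc.) until disease progression".

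**The follow-up that is scheduled.**
- Tables 4 and 5: the tumor-scan row is marked at Screening, at Day 1 of Cycle 2 and beyond, and at End-of-Study. The Two Monthly Follow-Up column is blank for scans.
- Section 9.4 lists two items: survival status and "Subsequent therapies for breast cancer".
- Section 12.1: after treatment stops, patients are followed for safety to 28 days "and for survival status by telephone (at approximately two monthly intervals, until death".
- Section 9.3: one scan at End-of-Study, 28 ± 7 days after the last dose. It may be skipped if the last scan was under 2 weeks earlier or already showed progression.

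**When the trial ends.** Section 5.1.3, repeated in SAP 2.2.3: "The trial will be completed when all enrolled patients have discontinued treatment and completed the end-of-study follow-up visit". Section 5.1.4 instead runs survival follow-up "until death or sponsor decision to end the trial, whichever comes first".

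**How PFS is censored.** Protocol 11.2.4.1 and SAP 12.1.1 censor patients without an event at the last adequate radiologic assessment. Neither has a separate rule for stopping before progression or for starting new therapy, and neither specifies a sensitivity analysis.

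**The concern.** The primary endpoint needs scans that have no visit attached to them. Patients can leave treatment without radiographic progression for several reasons: toxicity, clinical progression, non-compliance or investigator decision. A site working from the tables, 9.4 and 12.1 would scan such a patient once, at End-of-Study, and afterwards collect only survival and later therapies. PFS is then censored at or before that scan unless a death is recorded. If patients who stop progress sooner than those who stay on treatment, Kaplan-Meier overstates PFS.

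The completion rule adds to this. Read literally, 5.1.3 closes the trial at the last patient's 28-day visit. That ends both the off-treatment scans of 9.5.2.1 and the survival follow-up of 5.1.4 and 12.1, although late deaths could recover some missed PFS events.

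**Working it through.** **1. The plan's own precision figure.** From Protocol 11.3 and SAP 3: N = 80, observed 6-month PFS 50%, 90% CI.
- Half-width = 1.645 × √(0.5 × 0.5 / 80) = 0.092.
- Interval: 40.8% to 59.2% (Clopper-Pearson 40.3% to 59.7%).

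The stated claim (half-width under 10 points, lower limit above 40%) reproduces. The margin over 40% is 0.8 point (0.3 by Clopper-Pearson).

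**2. Size of the bias if scanning ends at the 28-day visit.** The documents give neither the share q stopping before progression nor the hazard multiplier k after stopping, so both are assumed.

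Model:
- On-treatment PFS is exponential with a 4-month median (the protocol's threshold): λ = ln 2 / 4 = 0.1733 per month.
- Stopping without progression is a competing exponential with hazard γ = λq/(1 − q).
- After stopping, the hazard is kλ.
- The last scan is 4 weeks after stopping, with censoring there if there is no event.
- 400,000 simulated patients.

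The true 6-month rate has a closed form:

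S(6) = e^(−6(λ+γ)) + γ·e^(−6kλ)·(e^(6d) − 1)/d, with d = (k − 1)λ − γ.

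For q = 20% and k = 2:
- γ = 0.1733 × 0.2/0.8 = 0.0433 and d = 0.1300.
- First term: e^(−1.300) = 0.273.
- Second term: 0.0433 × 0.125 × (2.181 − 1)/0.1300 = 0.049.
- Sum: 0.322 (simulated 0.323).
- Kaplan-Meier with scans ended: 0.343, an overstatement of 2.0 points.

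Overstatement of the 6-month PFS rate, in points:

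| q | k = 1 | k = 1.5 | k = 2 | k = 3 |
|---|---|---|---|---|
| 5% | 0.1 | 0.3 | 0.5 | 0.7 |
| 10% | 0.0 | 0.6 | 1.0 | 1.3 |
| 20% | 0.1 | 1.3 | 2.0 | 2.7 |
| 30% | 0.0 | 2.0 | 3.2 | 4.1 |

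The k = 1 column is zero within simulation error. Deaths are not modelled separately, so these figures may overstate the bias where deaths are captured.

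**3. Variant without the End-of-Study scan.** Events are dated at scheduled scans and stoppers are censored at their last scheduled scan. For q = 10% to 30%, the error is +0.7 to +4.8 points at k = 2 to 3, but −0.5 to −2.0 points at k = 1. The size is similar, but the direction depends on prognosis after stopping.

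**4. Does the loss of patients break the stated precision?** Treating each censored patient as contributing nothing gives 1.645² × 0.25 / 0.10² = 67.6, so 68 patients are needed and only 80 − 68 = 12 can be lost. Kaplan-Meier, however, uses each patient up to censoring. With N = 80, exponential PFS at 50% and Greenwood 90% intervals, the mean half-width is about 9.7 points with 15% (12 patients) censored before 6 months, 10.0 at 20% (16) and 10.6 at 30% (24).

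**The case against.** **The obligation is stated more than once.** It is in the synopsis and 9.5.2.1. The table footnote runs scans to disease progression, not to end of treatment. Appendix A asks that progression be documented even after discontinuation. This stands in part: the schedule is silent about off-treatment scans and does not forbid them. But the footnote ties the scans to cycle days, which no longer exist once a patient is off treatment, and neither 9.4 nor 12.1 picks them up. Appendix A itself says scheduled re-evaluation after treatment is warranted when time to an event is the main endpoint.

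**The exposure may be small.** One off-treatment scan is mandated, and later deaths count as PFS events. The clinical safety summary in Protocol 3.6.1.3 says adverse events rarely led to discontinuation, with 2.3% for each of the two most common causes. All of this stands and limits the size. It does not cover stopping for clinical decline, non-compliance or investigator decision, and the 5.1.3 rule could leave later deaths uncollected.

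**Three stronger readings that the documents do not support.**
- A reader might infer that losing 12 of 80 patients breaks the stated precision. Step 4 shows it does not.
- A reader might infer that these patients are typically censored just before they progress. Nothing in the documents shows this.
- A reader might infer that overall survival is biased. Section 5.1.4 already allows the sponsor to end the trial. An administrative cut-off shortens follow-up but is not informative in itself.

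**Conclusion.** The passages conflict and should be reconciled. Scans to radiographic progression are required after treatment stops, but no visit after End-of-Study provides for them, and the completion rule contradicts 9.5.2.1, 5.1.4 and 12.1.

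The consequence for primary PFS is a risk, not an established bias. It is essentially nil if stopping is unrelated to prognosis. It is about 1 to 4 points on the 6-month rate if 10% to 30% stop before progression and their hazard doubles or triples, and less where later deaths are recorded.

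Set against the 0.8-point margin in the protocol's example, that is enough to change the reading of a close result. The comparison shows order of magnitude only. The simulation uses a 4-month median (a 6-month rate of 0.5^(6/4) = 35.4% without early stopping), whereas the example assumes 50%. The criterion for further study also uses the observed median or rate, not the lower limit. The stated precision itself is correct and is not in dispute.

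**What to change.** 1. In the follow-up columns of Tables 4 and 5, and in Sections 9.4 and 12.1, add tumor scans for patients off treatment without progression, on the same calendar schedule until radiographic progression.
2. In Section 5.1.3 and SAP 2.2.3, align completion with 9.5.2.1 and 5.1.4: the last required scan or survival contact, or the sponsor's decision to end the trial.
3. If follow-up has already closed, have the SAP report how many patients stopped before progression, and add a sensitivity analysis of their censoring.

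The cost is wording and table edits plus somewhat longer follow-up for some patients. Items 1 and 2 add no obligation beyond 9.5.2.1 and 5.1.4. Item 3 is a small addition to the analysis.
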